4 RESEARCH QUESTION / AIM(S)

4.1 Aims

The aim of the HORIZONS Programme is to:

- Establish a series of cohorts of cancer patients to capture their health related outcomes and experiences from beginning active treatment and regularly over their life-course.
- Maintain and develop the HORIZONS Programme as a national and international resource to explore consequences of different cancer diagnoses and treatments from the individual perspective across the life-course.
- Inform policy and practice based innovative solutions to minimise the health burden and maximise support available to them over their life-course.

The key research questions are:

- What impact does cancer and its treatment have on people diagnosed with cancer in the short, medium and long term?
- What are the health outcomes, experiences and self-management activities over the life-course across different cancer types and what influences these?
- How do people connect with and mobilise resources which enable them to self-manage consequences of cancer and its treatment?

4.2 Key HORIZONS outcomes

By carefully capturing evidence prospectively and over time about cancer survivors' life histories we will be in a position to understand what consequences are faced, when and what can be done to improve the lives of people living with and beyond cancer.

The Macmillan HORIZONS evidence will:

- Improve understanding of the consequences of different cancers and treatments, impact of co-morbidities, impact of recurrence and late effects, characteristics that lead to increased risk of poor recovery, ability to self-manage and what helps or hinders this.
- Enable us to predict who is most likely to need support and what form this should take and when it should be available.
- Help to prepare future patients for likely consequences and how long these might last following treatment so that they know what to look out for and when to seek support. And to support decision making where appropriate.
- Support the transformation of care for people living with and beyond cancer. Better information on short, medium and long term outcomes and experiences across cancer types and treatments will enable

health professionals to provide more personalised care to their patients tailored to their needs and to support people to live as healthy and active a life as possible.

- Inform the development of risk stratification models such as likely proportion of patients in different follow-up pathways across cancer / treatment type.
- Identify areas for service innovation and other solutions to support cancer survivors and their personal networks to manage the consequences of cancer and its treatment across all aspects of their lives.
- Be an important vehicle for the development of further important clinical / research questions and development of theoretical models.

5 STUDY DESIGN, METHODS OF DATA COLLECTION AND ANALYSIS

5.1 Type of design

A series of longitudinal cohort studies will be conducted in cancer survivors using a questionnaire survey, either mailed or completed online.

Qualitative work is planned during the Programme and once details are known will be submitted as a protocol amendment. Patients will give consent to be approached about other related studies at initial consent and those who consent will be contacted to ask if they would like to participate in related qualitative studies. Full information will be given and additional consent to participate in these studies will be taken prior to any data collection.

5.2 Study measures

The validated measures used will be informed by the conceptual framework (Figure 1) and some study-specific questions will be developed. Not all measures will be used at each time-point.

A core set of measures will be administered at each time-point across all cancer types. A small number of tumour-specific measures will be included to capture disease-specific consequences. See Table 1 for proposed measures. Consent will be sought to collect medical details for all participants.

From summer 2020 for a 12 month period, an insert of COVID-19 questions will be included with the next questionnaire booklet each participant receives (at one time point only for each participant). This is necessary to help us understand any differences in responses to the main HORIZONS questionnaires completed before and after the pandemic. In addition, these questions will help us understand the needs of people being treated for and recovering from cancer during the pandemic.

5.2.1 Primary outcome measure

QLACS; [26] will be the primary outcome measure across cancer types and will be included at each time-point. QLACS [26] was developed to assess QoL of adult cancer survivors. QLACS measures 12 domains of cancer survivorship; 7 generic domains (pain, fatigue, positive and negative feelings, cognitive and sexual problems, social avoidance) and five cancer-specific domains (financial problems, family distress, recurrence distress, appearance concerns, benefits from cancer). QLACS has been validated amongst cancer survivors [26] and has good convergent validity with other QoL measures (e.g. FACT and SF36).

Areas under investigation will include (see Table 1 for details):

- Pre-existing factors: including age, gender, social circumstances, co-morbidities.
- Cancer diagnosis and treatment (data collected on medical details form by participating centres).
- Consequences of cancer diagnosis and treatment: including physical symptoms, psychological problems, social implications such as impact on social relationships and networks, practical implications (e.g. work-related problems, everyday chores, travel); perceived impact on everyday life including financial impact, and how this is experienced as burdensome to individuals.
- Self-management of consequences and aftercare: self-management activities.
- Personal factors: Individual characteristics such as reliance and confidence to self-manage; perceived burden of treatment; perceived support and resources that individuals have in order to manage consequences for themselves.
- Environmental factors: access to / utilisation of health and social care and other forms of support, including social support through family, friends, community, healthcare, social care, third sector and social networks
- Health and well-being: quality of life, health status, personal well-being.
- Life events.

Medical details: Clinical information, such as cancer type, stage, treatment, co-morbid conditions, height and weight, will be abstracted from clinical records by the nurse / researcher at the participating centre. Change in health condition and treatment will be monitored through self-report at follow-up and further collection of clinical data from participating centres at regular intervals throughout the Programme.

Table 1: Proposed questionnaire measures according to domains of the theoretical framework

Domain	Areas of assessment	Proposed measures*
Pre-existing factors	Socio-demographic (age, gender, neighbourhood deprivation (calculated from postcode), housing status, vehicle ownership / use, sexual orientation)	
	Educational attainment	Highest level achieved
	Domestic situation (marital status, who lives with participant, number of children / dependents)	
	Caring responsibilities	
	Ethnicity	
	Occupational / economic factors (employment status, household income, weekly hours, sickness leave, history of shift working, receipt of benefits / pension)	
	Access to mental health services	
	Family history of cancer	
	Genetic testing for cancer	
	Co-morbidities	List of current co-morbidities and impact on everyday activities
	Lifestyle:	
	- Exercise	Godin-Shepard Leisure-Time Exercise Questionnaire; Resistance and strength exercise questions

	- Diet	Fruit and vegetables screening log; special diet open-ended question
	- Smoking; including use of e-Cigarettes	Whether current / ex- / non-smoker and amount for current / ex-smokers; similar questions used for e-Cigarette use
	- Alcohol	Frequency of alcohol drinking and number of units
Consequences of cancer diagnosis and treatment	Symptoms, functioning	European Organisation for Research and Treatment of Cancer (EORTC) QLQ-C30 and tumour-specific modules (see Appendix 3)
	Body image	Body Image Scale (BIS)
	Sexual functioning	In EORTC tumour-specific modules
	Sleep problems	
	Anxiety and depression	Hospital Anxiety and Depression Scale (HADS)
	Impact on day to day tasks	Work and Social Adjustment Scale (WSAS); in EORTC tumour-specific modules
	Financial impact	Captured by EORTC QLQ-C30 subscale; self-report on financial cost of accessing health and social care services (e.g. petrol, parking, public transport) and other costs associated
	Burden of treatment	Patient Experience with Treatment and Self-management (PETS)
	Fear of recurrence	Worry of Cancer scale; captured by QLACS subscale
	Unmet needs	Supportive Care Needs Survey (SCNS)
Positive outcomes / benefits of cancer	Captured by subscale in QLACS part 2	

Self-management of consequences and aftercare	Self-management	Health Education Impact Questionnaire (heiQ)
	Use of internet	
	Use of other therapies (including complementary and alternative medicines)	
	Use of follow-up and routine health assessments	
Personal factors	Self-Efficacy	Self-Efficacy for Managing Chronic Disease Scale (Lorig) – Cancer survivors version
	Resilience	Brief Connor-Davidson Resilience Scale (CDRISC2)
	Health literacy	Brief Health Literacy Screen (3 questions)
	Health beliefs	Brief Illness Perception Questionnaire (BIPQ)
Environmental factors	Access to / utilisation of health and social care and third sector; including receipt of advice or information	
	Patient experience of care	
	Social support and social networks	Medical Outcomes Study (MOS) Social support scale; adapted UCNET (mapping tool)
Health and well-being	QoL	QLACS, parts 1 and 2
	Health status and Well-being	EuroQoL EQ-5D-5L and Visual Analogue Scale; SF-12 version 2 (SF-12v2)
Life events	Significant life events	Open-ended question

* Where there is no named questionnaire measure given, study-specific questions will be used that have been developed from existing studies, including others conducted by the MSRG and also utilising national resources, e.g. from the Office for National Statistics (ONS).

5.3 Collection of Data - schedule of data collection

Baseline data will be collected by direct approach to ALL eligible patients from the recruiting clinician / research nurse PRIOR to primary treatment and assigned as time T₀. One of the criteria for selecting participating centres to participate in HORIZONS will be the ability to approach a total sample and prior to treatment commencing. Outcome data will be collected at regular intervals and these timings will be consistent across the different cancer types. Participants will have the option to complete paper-based or online questionnaires. All follow-up questionnaires will be sent to participants from the HORIZONS Coordinating Centre in Southampton.

Timing of assessments will be refined during the set up phase following wide consultation.

Proposed assessment points:

T₀: baseline – following diagnosis but prior to initial curative intent treatment

T₁: 3 months after study entry – to monitor early adaptation and coping and detect initial treatment effects.

T₂: 12 months after study entry – to monitor later adaptation and coping and detect initial treatment effects.

T₃: 18 months after study entry – to monitor further adaptation and early stages of recovery

T₄: 24 months – to monitor consequences in the longer term and how they are managed.

T₅ +: Annual assessments to monitor consequences, emergence of late effects, co-morbidities, lifestyle change and how they are experienced and managed across the life-course.

5.4 Methods of data collection

Data will be collected through:

- Self-report questionnaires over the course of the HORIZONS Programme; prior to treatment and in the months and years beyond.
- Routinely collected medical records data. Medical details will be collected via CRFs at baseline, 6 months, 12 months and then annually by research nurses at the participating centres.

Procedure for Study Questionnaires:

Baseline and follow-up data will be collected using self-report questionnaires. Patients will be given the option of completing the questionnaires either on paper or online (from T₁). The paper baseline questionnaire will be given directly to the patients in clinic to be returned to the HORIZONS Coordinating Centre using the pre-paid envelope provided. A paper copy of the T₁ questionnaire will be mailed directly to participants together with instructions outlining optional online completion using a secure web-portal. Participants can choose to complete subsequent questionnaires online, with email reminders when due. If participants do not respond to email reminders they will be sent a paper copy of the questionnaire. If a participant completes their paper questionnaire at any time-point and returns it using the pre-paid envelope, it will be assumed this is how they would like to receive further questionnaires but the option for online completion will still be offered each time.

The baseline questionnaire will be completed prior to initial primary curative intent treatment (the date of questionnaire completion will be compared to date of treatment to establish this). If the patient is unable to complete the baseline questionnaire then **in exceptional circumstances only**, patients will not complete the

baseline but will be sent follow-up questionnaires if they are willing to participate providing the HORIZONS Coordinating Centre is informed.

On receipt of returned questionnaires these will be checked for completeness. Participants will be contacted by the HORIZONS Coordinating Centre (for example by telephone, email, letter) to ask about whether sections were missed in error and if possible complete missing items in order to reduce the amount of missing data. Mailing of paper questionnaires, or an email reminder to participants electing to complete questionnaires online, will take place within three weeks of the due date of assessment to aim for data collection to be completed as close as possible to the specified assessment date. Participants will be asked to record the date of completion of questionnaires. Prior to contacting participants regarding completion of the next questionnaire the participants' clinical team will be contacted to request confirmation that the participant is alive and the participants' address has not changed. If the clinical team are unable to confirm whether the participant is alive and has not moved by the due date of assessment and all reasonable efforts to acquire this information in a timely fashion have been explored (e.g. GP contact, other hospital sites), the questionnaire will be sent with a notice informing the participant that their status was not confirmed prior to contact. Participants will also be advised to contact the Coordinating Centre if their information has changed or is not correct. The same follow-up protocol for non-response will be followed at each time-point (see consent and non-participation and withdrawal, sections 7.5 and 7.6).

Medical details CRF

The medical details CRF will be completed by the clinical team / researcher at baseline, six and twelve months and then annually for all patients who provided consent. Information including cancer type, stage, treatment, co-morbid conditions, recurrence and survival will be abstracted from clinical records. As part of the extended follow-up, brief medical information will be collected via self-reported medical status questions on follow-up questionnaires.

5.5 Analysis

For Theme 1: Recovery from cancer treatment

Descriptive statistics will be used to characterise the primary outcome of Quality of Life (QLACS) and describe health status (EQ-5D-5L) and symptoms / functioning (EORTC QLQ C30 and tumour-specific modules) over time. Changes in these outcomes over time will be investigated using longitudinal methods including generalised estimating equations, and group-based trajectory analyses will investigate whether there are distinct subgroups of recovery within each cohort. Factors that may influence recovery will be included in the regression models, including cancer and treatment type, socio-demographics, treatment and symptom burden, social support, personal dispositions, self-efficacy, self-management, personal network support, lifestyle, comorbidities, utilisation of health and social services, and recurrence. The varying contribution of these factors will be assessed to determine which have the most influence on the outcomes of quality of life, health status, well-being and symptoms / functioning following treatment. Recurrence and survival (overall and disease-specific) will be analysed using standard methods of survival analysis, such as Kaplan-Meier analysis.

Using data from National Databases

In order to evaluate whether the HORIZONS samples are representative of the national population in terms of sociodemographic and clinical characteristics, we will request data from national cancer registries to allow for aggregate comparisons. Requests will be made to Public Health England, ISD Scotland, Welsh Cancer Intelligence and Surveillance Unit and the Northern Ireland Cancer Registry.

In addition, we will request data at the individual level from the same organisations for participants who provide consent to link the data collected by HORIZONS with the data held on national databases. These data will allow additional clinical information to be collected.

For Theme 2: Self-managing the consequences of cancer

Descriptive statistics will be used to summarise patients' self-management activities, and their capacity and confidence to self-manage problems, and longitudinal analyses as previously described will assess changes over time in the measures of self-management (heiQ). Factors that may influence self-management will be investigated in the regression models, such as capacity to self-manage, social networks and community support, utilisation of health and social services, cancer recurrence and co-morbidities. Analyses will also explore how self-management relates to recovery of quality of life, health and well-being. Self-management activities will be compared across groups including cancer and treatment types using statistical methods already described, and analyses such as group-based trajectory analyses will investigate whether there are distinct subgroups with different follow-up care needs.

Patterns of missing data will be investigated in the analysis.

Quantitative data will be analysed using statistical packages such as SPSS and Stata.

6 STUDY SETTING

We aim to recruit people diagnosed with cancer amenable to treatment with curative intent through their clinical teams prior to primary treatment. Participants will be identified and recruited from NHS treatment centres across the UK, with centres chosen from those who express an interest through the CRN or directly to the HORIZONS Coordinating Centre. Centres will be selected for their proven research capability in these cancer types. Centres will indicate that they can approach a TOTAL SAMPLE of eligible patients and BEFORE TREATMENT begins. Additionally, Centres will be selected to ensure the Study covers a wide range of geographical locations across England, Scotland, Wales and Northern Ireland, ethnically diverse populations and varying-sized hospitals.

7 SAMPLE AND RECRUITMENT

7.1 Eligibility Criteria

For each cancer type, we aim to recruit all newly diagnosed patients who will be treated with curative intent (based on imaging, clinical, cytological or histological diagnosis) for the included cancers through their clinical teams prior to primary treatment. The generic inclusion/exclusion criteria for the Study are below, the specific requirements for each cohort are found in Appendix 4.

Diagnosis may not be confirmed until after treatment has begun (i.e. after surgery), if a participant's status (e.g. staging) changes after confirmed diagnosis they will be reassessed for eligibility. If patients meet any exclusion criteria (e.g. surgery reveals their cancer was from another origin site) they will be excluded and no further data will be collected. Participants will be informed by a member of their clinical team that they are no longer eligible to participate.

7.1.1 Inclusion criteria

To be included, patients must:

- Have a new diagnosis of one of the selected cancer types determined through clinical assessment, cytology, histology or imaging
- or
- Have new / second primary cancer at a site previously treated for cancer.
- Be awaiting primary **curative intent** treatment, including neoadjuvant treatment.
- Be ≥ 16 years old.
- Be able to complete questionnaires in English.
- Be able to provide written, informed consent.

7.1.2 Exclusion criteria

Patients will be excluded if:

- They do not have one of the specified cancer types
- Disease is recurrence / progression (either locally advanced or metastatic) at an existing cancer site.
- They are having treatment for a potentially curative recurrence of disease e.g. locally advanced disease (i.e. they have been previously treated for the same cancer).

- They have metastatic disease from a cancer¹ at another site
- They have synchronous primary cancers involving two or more of the HORIZONS specified cancer types²

7.2 Sampling

7.2.1 Size of sample

Sample size calculations are based on the primary outcome measure (QLACS). The mean generic summary score for QLACS is 71.2 (SD 25.6) [26]. A difference of one half of a standard deviation is often quoted as a minimum clinically important difference in sample size calculations: using 80% power to detect a difference of one half of a standard deviation at the 0.05 significance level would require a minimum of 228 participants per cancer type, assuming unequal-sized groups will be compared in the analyses. Assuming an intra-cluster correlation of 0.05 to allow for similarities between participants from each participating centre and an average of 30 participants per participating centre the cluster correction increases this figure to 559 per cohort. Taking into account 10% withdrawal and a range of five year survival rates according to cancer type, and rounding up to allow for some subgroup analyses results in approximately 1,000 participants per cancer type.

The sample size will be sufficient for other continuous measures, assuming the same size of difference (one half a standard deviation). Subgroup analyses within cancer types will be possible, but numbers will be small for some instances, limiting the conclusions that can be drawn from these.

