Key Protocol Contributors	
[name], [name], [name], [name], [name], [name], [name] Macmillan Survivorship Research Group School of Health Sciences University of Southampton [name] [name] Email: [contact]

Strategic Advisory Board Members	
Chair: [name] [name], Pro-Vice-Chancellor (PVC) for Research and Knowledge Exchange University of Nottingham
 
Members: [name], Consultant in Medical Oncology, University Hospitals Southampton [name], Reader in Cancer Care and Lead for eHealth, University of Surrey

	
[name], Professor of Social Statistics, Director of the ESRC Administrative Data Research Centre for England, Deputy Director of Southampton Statistical Sciences Research Institute, University of Southampton
 
[name], Specialist Advisor, Treatment and Recovery in Cancer Care, Macmillan Cancer Support
 
[name], Medical Adviser, Macmillan Cancer Support
 
[name], Professor of Epidemiology, University of Bristol
 
[name], Director of Centre for Population Health Sciences, University of Edinburgh
 
[name], Professor of Psychosocial and Medical Oncology, University of Leeds
 
[name], Professor of Oncology, Imperial College, London
 
[name], Chair NCRI Consumer Liaison Group
 
[name], Senior Programme Manager, NHS England
 
[name], Clinical Professor in Cancer Nursing and End of Life Care, University of Southampton
 
[name], Founding Director, Northern Ireland Cancer Registry
 
[name], Consultant Medical Oncologist, Beatson West of Scotland Cancer Centre and Honorary Clinical Senior Lecturer, University of Glasgow

--	---

STUDY SUMMARY

Study Title	HORIZONS: a cohort study to explore recovery of health and well-being in adults diagnosed with cancer
Internal Ref. No. (or short title)	Macmillan HORIZONS Programme
Study Design	Prospective cohort study
Study Participants	Participants will be individuals diagnosed with non-metastatic cancer, identified through their clinical teams, prior to primary treatment. Participants will be recruited from NHS treatment centres across the UK, with centres chosen from those who express an interest through the Clinical Research Network (CRN) or directly to the study team in Southampton.
Planned Size of Sample (if applicable)	3000 participants

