11.3 Appendix 3 - Proposed tumour-specific measures for each cohort

Domain	Areas of assessment	Breast	NHL	Gynaecological
Consequences of Cancer Diagnosis and Treatment	Symptoms, functioning, short and long-term adverse effects	EORTC QLQ-BR23	EORTC QLQ-NHL-HG29 (NHL high grade) and QLQ-NHL-LG20 (NHL low grade)	EORTC QLQ-CX24 (cervical), QLQ-EN24 (endometrial), QLQ-OV28 (ovarian), QLQ-V31 (vulval)
	Additional adverse effects not captured on EORTC tumour-specific modules, such as:	Neuropathy (use items from other tumour-specific modules)		
		Radiotherapy-specific adverse effects Sleep problems Fertility problems Urinary and bowel problems Osteoporosis		

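### The statement that the sample suffices for other continuous measures does not hold for all four site-specific gynaecological modules, each of which only part of one cohort completes

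*Protocol*

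**What the plan says.** Protocol section 7.2.1 sizes the study on the primary outcome, QLACS: "The mean generic summary score for QLACS is 71.2 (SD 25.6"). The target is set "using 80% power to detect a difference of one half of a standard deviation at the 0.05 significance level", which it says "would require a minimum of 228 participants per cancer type, assuming unequal-sized groups will be compared in the analyses". A cluster correction (intra-cluster correlation 0.05, 30 participants per centre) raises 228 to 559 per cohort. Allowing for 10% withdrawal, deaths and some subgroup work then "results in approximately 1,000 participants per cancer type". The study summary gives the total as "3000 participants".

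The section then extends the result to other outcomes: "The sample size will be sufficient for other continuous measures, assuming the same size of difference (one half a standard deviation"). The sentence after that warns that subgroup analyses within cancer types will have small numbers in some instances.

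Appendix 3 (section 11.3) assigns the gynaecological cohort four different questionnaires: "EORTC QLQ-CX24 (cervical), QLQ-EN24 (endometrial), QLQ-OV28 (ovarian), QLQ-V31 (vulval"). The breast cohort has one module. Section 5.5 lists among the Theme 1 outcomes "symptoms / functioning (EORTC QLQ C30 and tumour-specific modules) over time". The protocol gives no target number or expected split for the four gynaecological sites.

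**The concern.** A total of 3,000 at about 1,000 per cancer type leaves room for three units, so gynaecological cancer counts once. A cervical module score exists only for women with cervical cancer, and likewise for the other three sites. The cohort of 1,000 is therefore never the denominator for any of these outcomes, yet the sufficiency sentence covers all other continuous measures without exception.

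At stake is how null results are read. A non-significant comparison on one of these modules could be reported as coming from a study with 80% power for half a standard deviation when the number behind it does not provide that.

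**Working it through.** **Inputs from section 7.2.1:** difference 0.5 SD, power 80%, significance level 0.05 (taken as two-sided), 228 before clustering, intra-cluster correlation 0.05, 30 per centre, 10% withdrawal, about 1,000 per cohort.

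**Inputs not in the protocol:** group ratio, split between sites, survival rates. These are inferred or assumed below.

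**1. The plan's own figures.** For groups in ratio r:1, the smaller group needs (1.96 + 0.84)² × (1 + 1/r) / 0.5².
- Totals for 1:1, 2:1, 3:1 and 4:1 are 126, 144, 168 and 200.
- At 5:1: 7.85 × 1.2 / 0.25 = 37.7, so 38 + 190 = 228. This matches the plan exactly.
- Design effect: 1 + (30 − 1) × 0.05 = 2.45, and 228 × 2.45 = 558.6, so 559. This also matches.

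**2. Four modules, no clustering.** 4 × 228 = 912 analysable. After 10% withdrawal the cohort has at most 1,000 × 0.9 = 900, before deaths. All four cannot reach 80% under any split.

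**3. Four modules, with clustering.** If a site holds a share s of the cohort, its cluster size is about 30s and its design effect is 1 + (30s − 1) × 0.05 = 0.95 + 1.5s. It then needs 228 × (0.95 + 1.5s).
- Summed over four sites whose shares add to 1: 228 × (3.8 + 1.5) = 228 × 5.3 = 1,208, whatever the split.
- At an equal split, cluster size is 7.5, design effect 1.325 and the need 302 per site, against 225 available.

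**4. Share that one site needs.** Set 900s = 228 × (0.95 + 1.5s). Then 558s = 216.6 and s = 0.39. Three sites would need 117% of the cohort, so at most two of the four can reach 80% on this basis.

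**5. Power at an assumed equal split.** With 225 analysable per site before deaths and 5:1 groups, power = Φ(0.5 × √(n_eff × 5/36) − 1.96):

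| Cluster size | Design effect | Effective n | Power |
|---|---|---|---|
| 30 (not scaled) | 2.45 | 92 | 43% (42% by t test) |
| 7.5 (scaled) | 1.325 | 170 | 68% |
| 3.2 (250 spread over 78 centres) | 1.11 | 203 | 76% |

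The detectable difference at effective n 170 is 2.80 / √(170 × 5/36) = 0.58 SD.

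**6. Smaller sites and deaths.**
- A site with an assumed 10% of the cohort (90 analysable, scaled clustering) has 39% power; one with 5% has 23%.
- If all the loss from 1,000 to 559 were attrition, an equal split would leave about 140 per site and 48% power with scaled clustering. This overstates the loss, because the 1,000 also contains rounding up for subgroups.

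**7. Sensitivity to the group ratio.** Repeating step 3 with the other totals gives, for all four modules, 126 × 5.3 = 668 (1:1), 144 × 5.3 = 763 (2:1), 168 × 5.3 = 890 (3:1) and 200 × 5.3 = 1,060 (4:1), against 900 before deaths. For a 1:1 contrast at an equal split, power is about 90% before deaths and 73% at 140 per site.

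**8. Whole-cohort measures.** At 5:1 with design effect 2.45, 559 analysable give 80% and 900 give 95%. The plan's claim holds there.

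**The case against.** The strongest reply is that section 7.2.1 already discloses the limit in its next sentence. If the cohort is the unit, the gynaecological sites are subgroups within it; Appendix 2 itself calls vulval cancer a sub-cohort. A module given to one site can only be analysed within that site, so the caveat can be read as reaching it. Part of this stands: a careful reader is warned that some numbers will be small. But the caveat concerns subgroup analyses. Analysing a module in everyone who receives it is the full analysis of that outcome, and the caveat neither gives numbers nor withdraws the sufficiency statement.

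A second reply is that the 5:1 ratio is inferred and the site split is unknown. That is correct, and it matters. With balanced or mildly unequal groups and favourable shares, the modules could reach 80% before deaths. The plan, however, sizes the study for unequal groups, and 5:1 is the ratio that reproduces its 228, so the claim is fairly judged on that basis.

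Three stronger readings are tempting and are not supported:
- **That the statement fails for tumour-specific modules in general.** Breast has a single module for its whole cohort. Lymphoma lists two, but eligibility in Appendix 4 is diffuse large B-cell lymphoma, so no split of that cohort is shown.
- **That each site needs 559.** That figure keeps 30 patients per centre for a single site, which would put 250 recruits in about eight centres when section 7.3 plans 78. Cluster size should shrink with the subset.
- **That the plan claims 80% power for each of the four gynaecological cancers.** Section 7.2.1 uses *per cancer type* and *per cohort* for the same unit, and a total of 3,000 fits only three.

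**Conclusion.** The sufficiency statement is wrong as written for the set of four gynaecological modules. The plan's arithmetic for QLACS is sound; the fault lies in extending it without qualification to outcomes that only part of a cohort can provide.

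On the plan's own basis the shortfall is 912 against 900 with no clustering, and about 1,208 against 900 with scaled clustering, both before deaths. Neither comparison depends on how the 1,000 divide between sites; both depend on the 5:1 ratio implied by 228. The power of about 68% per module (roughly 42% to 76% across cluster sizes of 30 to 3) also assumes an equal split and no deaths. A balanced comparison in a larger site could still reach 80%, so the finding is that the claim does not hold for all four modules, not that every module comparison is underpowered. The primary outcome and every measure shared by a whole cohort are untouched.

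**What to change.** In section 7.2.1:
- limit the sufficiency statement to measures completed by a whole cohort;
- say that it does not extend to the site-specific gynaecological modules;
- give the expected number of participants and the detectable difference for each gynaecological site, with the group ratio and cluster size used;
- write *per cohort* throughout in place of *per cancer type*.

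This costs a few sentences and requires no extra patients and no change to data collection. The stated claim becomes less favourable.
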